4.4 Expansion Part

The aim of the expansion part is to provide further data on the safety, tolerability, PK and antitumor activity of the selected dose regimen(s).

The expansion cohorts may run in parallel. Each cohort will only contain one selected indication on a specific dose regimen. More than one dose regimen per indication may potentially be evaluated, depending on the outcome from the escalation part. Within an indication these would all constitute different expansion cohorts, and patients would in this case be randomized between the available dose regimens (see Section 6.1.2 on treatment assignment for more information). A total of up to seven expansion cohorts will be opened.

In each expansion cohort, an analysis after at least 10 evaluable patients will be performed. If there is evidence of anti-tumor activity such as tumor shrinkage or prolonged disease stabilization, and without safety concerns, up to 60 patients will be allocated to an expansion cohort in a stage wise fashion, primarily testing pre-specified futility criteria (see Section 11.7 for further details), but also taking the totality of the data into account. The data will be evaluated by the sponsor safety committee which decides on further recruitment into the cohort.

A DMC review of safety data will be performed when 12 patients have been recruited and have been followed for at least two cycles (regardless of indication and dose regimen). DMC safety review will be performed after 36 patients have been recruited and followed for at least two cycles (regardless of indication). Thereafter, DMC safety review will be performed at least quarterly. The DMC and the sponsor safety committee will evaluate the safety profile with particular emphasis on any safety signals.

Patients in the expansion part will be treated on the dose regimen(s) from the dose escalation part recommended by the DMC and confirmed by the sponsor safety committee based on a positive benefit-risk assessment. If deemed appropriate, and based on data available, the expansion part may be initiated before the MTD has been reached. Furthermore, different doses and regimens might be explored in the expansion cohorts.

4.5 Planned Number of Patients

The dose escalation part will enroll up to approximately 100 patients shared between the Biweekly and Priming Regimens. Three patients were exposed in an Intensified Regimen (8xQ1W/Q2W) all of whom experienced DLTs and, consequently, this dosing regimen was permanently discontinued.

In the expansion part, the planned number of patients depends on how many indications and regimens that will be evaluated. Each opened cohort (which is indication and regimen specific) will enroll between 10 and 60 patients. Opening all seven cohorts would allocate between 70 (minimum 10 in each) and 420 (maximum 60 in each) patients in the expansion part.

4.6 Trial Design Rationale

Part I of this trial is a FIH, open-label, dose-escalation, safety trial studying the DR5-specific agonistic hexamer-forming antibody GEN1029 in patients with different types of malignant solid tumors in order to determine the MTD and/or RP2D the safety profile of GEN1029.

Escalation and de-escalation in the dose escalation part will be guided by a mBOIN design, which is very similar to the 3+3 design but with the possibility to investigate a dose level again that would have been closed in a 3+3 design after de-escalation to a lower dose level and observing that level to not be toxic. This greatly enhances the probability of identifying the correct MTD level.

Part II of this trial is the expansion part including up to seven indications for further investigation. The aim of the expansion part is to provide further data on the safety, tolerability, pharmacokinetic and anti-tumor activity of the selected dose.

4.7 First-in-Human Clinical Trial Starting Dose, dose increments and highest preplanned dose level

A First-in-Human clinical trial starting dose of **0.3 mg/kg** is proposed for GEN1029. This dose level is considered to be safe and in the lower end of the potential therapeutically active dose range, based on considerations from the following preclinical pharmacology, pharmacokinetic and toxicology studies:

,

44

Genmab

4.8 End of Trial and End of Treatment Definitions

4.8.1 End of Trial

The trial is considered completed with the last safety follow-up visit (70 days after last dose) for the last patient participating in the trial. The final data from the trial site will be sent to the sponsor (or designee) after completion of the final patient visit within the time frame specified in the clinical trial agreement. The trial will run for a maximum of three years after the last patient first treatment.

4.8.2 End of Treatment

For each patient the treatment period will be until progression (cycles of 14 days) unless the patient fulfills one of the discontinuation of treatment criteria (see Section 8.1).

4.8.3 Trial Termination

The sponsor reserves the right to close the trial site or terminate the trial at any time for any reason at the sole discretion of the sponsor. Trial sites will be closed upon trial completion. A trial site is considered closed when all required documents and trial supplies have been collected and a trial-site closure visit has been performed.

The investigator may initiate trial-site closure at any time, provided there is reasonable cause and sufficient notice is given in advance of the intended termination.

Reasons for the early closure of a trial site by the sponsor or investigator may include but are not limited to:

- Failure of the investigator to comply with the protocol, the requirements of the IEC/IRB or local health authorities, the sponsor's procedures, or ICH-GCP guidelines
- Inadequate recruitment of patients by the investigator
- Discontinuation of further trial drug development

5 TRIAL POPULATION(S)

5.1 Inclusion Criteria

Patients are eligible to be included in the trial only if all of the following criteria apply:

1. Patient must be ≥ 18 years of age, at the time of signing the informed consent.

2. For the dose escalation part:

Patients with advanced and/or metastatic CRC, NSCLC, TNBC, RCC, gastric (incl. esophagogastric junction), pancreas or urothelial cancer who have no available standard therapy likely to confer clinical benefit or who are not candidates for such available therapy, and for whom, in the opinion of the investigator, experimental therapy with GEN1029 may be beneficial.

For the expansion part:

Patients with advanced and/or metastatic cancer in up to seven of the following indications: CRC, NSCLC, TNBC, RCC, gastric, pancreas or urothelial cancer who have failed the following anticancer therapy for metastatic disease (if patients were eligible for the respective treatments):

- CRC: CRC patients after failure of at least 2 prior systemic regimens but not more than 4 for advanced and/or metastatic disease (adjuvant and maintenance treatment is considered being part of one treatment regimen) including but not limited to oxaliplatin- and irinotecan-containing regimens as well as EGRF and VEGF-A targeting antibodies, immune checkpoint inhibitors (PD-1 or PD-L1 inhibitor), capecitabine, ziv-aflibercept, ramucirumab, regorafenib, vemurafenib, and trifluridine-tipiracil.
- NSCLC: NSCLC patients after failure of at least 1 prior systemic regimens but not more than 3 for advanced and/or metastatic disease (adjuvant and maintenance treatment is considered being part of one treatment regimen) including but not limited to one platinum-containing regimen (or alternative chemotherapy due to platinum ineligibility, e.g. a gemcitabine-containing regimen) and failure of an immune checkpoint inhibitor (patients must have been treated with an approved PD-1 or PD-L1 inhibitor according to the established local label and access). Patients with epidermal growth factor receptor (EGFR) mutations or anaplastic lymphoma kinase (ALK) / c-ros oncogene 1 receptor tyrosine kinase (ROS1) rearrangement, or B-Raf proto-oncogene serine/threonine-protein kinase (BRAF) mutations should have been treated with appropriate targeted therapy before trial entry.
- TNBC: TNBC patients after failure of at least 1 prior systemic regimen for advanced and/or metastatic disease but not more than 4 (adjuvant and maintenance treatment is considered being part of one treatment regimen) including but not limited to anthracycline-, antimetabolite- or microtubule inhibitor-containing regimens, or PARP inhibitors
- RCC: RCC patients after failure of at least 2 prior systemic regimens for advanced and/or metastatic disease but not more than 3 (adjuvant and maintenance treatment is considered being part of one treatment regimen) including but not limited to anti-angiogenic agents, mTOR inhibitors and immune checkpoint inhibitors (patients must

have been treated with an PD-1 or PD-L1 inhibitor according to the established local label and access; unless contraindicated).

- Gastric cancer (incl. esophagogastric junction): gastric cancer patients after failure of at least 2 prior systemic regimens for advanced and/or metastatic disease but not more than 3 (adjuvant and maintenance treatment is considered being part of one treatment regimen) including but not limited to one platinum-containing regimen (or alternative chemotherapy due to platinum ineligibility) and failure of a taxane-containing regimen, ramucirumab or an irinotecan-containing regimen. Patients with PD-L1 positive tumors or HER2 overexpression should have been treated with appropriate targeted therapy before trial entry according to the established local label and access.
- Pancreas cancer: pancreas cancer patients after failure of at least 1 prior systemic regimen for advanced and/or metastatic disease but not more than 2 (adjuvant and maintenance treatment is considered being part of one treatment regimen) including but not limited to taxane-, antimetabolite- or platinum-containing regimens, or immune check-point inhibitors according to the established local label and access.
- Urothelial cancer: patients after failure of at least 1 prior systemic regimen for advanced and/or metastatic disease but not more than 3 (adjuvant and maintenance treatment is considered being part of one treatment regimen) including but not limited to one platinum-containing regimen (or alternative chemotherapy due to platinum ineligibility, e.g. a gemcitabine-containing regimen) and failure of an immune checkpoint inhibitor (patients must have been treated with an approved PD-1 or PD-L1 inhibitor according to the established local label and access).
- 3. Patients must have measurable disease according to Response Evaluation Criteria In Solid Tumors (RECIST) version 1.1.
 - A minimum of one lesion ≥ 10 mm (or twice the slice thickness if slices are not 5 mm thick) in the longest diameter (LD) from a non-irradiated area.
 - 1. Lymph nodes lesion \geq 15 mm in the shortest diameter from a non-irradiated area.
 - 2. If target lesion(s) are located within previously irradiated area patients can be enrolled if:
 - i. target lesions have not been irradiated within the last 3 months.
 - ii. there has been demonstrated progression in the "in field" target lesion and after sponsor acceptance.
- 4. In the dose escalation part all patients must provide a tumor tissue sample (Formalin Fixed Paraffin Embedded (FFPE) blocks/slides) from either archival tissue (preferably derived from advanced disease stage) or a fresh biopsy collected before Cycle 1, Day 1.

In the expansion part a mandatory fresh biopsy (FFPE tissue blocks/slides) at screening (aspirates are not acceptable) is to be provided for all patients which is taken after failure/stop of last prior treatment, unless not clinically feasible as documented by investigator. In case it is not feasible to meet the required criteria for a fresh tumor biopsy, the sponsor medical officer's approval of enrollment is needed. Furthermore, the latest available archival tumor tissue sample has to be collected if available.

5. Have an acceptable hematological status defined as:

- Hemoglobin \geq 5.6 mmol/L (~ 9 g/dL).
- Absolute neutrophil count (ANC) $\geq 1500/\mu L (1.5 \times 10^{9}/L)$.
- Platelet count $\geq 75 \times 10^9$ /L.
- 6. Have an acceptable renal function defined as:
 - Glomerular filtration rate (GFR) \geq 50 mL/min/1.73 m² e.g., according to the abbreviated Modification of Diet in Renal Disease (MDRD) equation:

 $GFR = 186 \times (SCr^{-1.154}) \times (age^{-0.203})$

(where SCr, the serum creatinine level, is expressed in mg/dL; multiply it by 0.742 if the patient is female; multiply it by 1.212, if the patient is African-American (Levey et al., 1999).

- Not being on dialysis.
- 7. Have an acceptable liver function defined as:
 - Alanine aminotransferase (ALT) and aspartate aminotransferase (AST) ≤ 3 times the ULN (independent of liver involvement).
 - Bilirubin $\leq 1.5 \times$ ULN (except in patients diagnosed with Gilbert's syndrome, who can have total bilirubin < 3.0 mg/dL), direct bilirubin $\leq 2 \times$ ULN.
- 8. Have an Eastern Cooperative Oncology Group (ECOG) performance status of 0 or 1
- 9. Body weight \geq 40kg.
- 10. Patients, both females and males, of childbearing or reproductive potential must agree to use adequate contraception as described below from the screening visit until six months after the last infusion of IMP.
 - Female trial participants of childbearing or reproductive potential must agree to use one of the highly effective methods of contraception described in Table 5-1 from the screening visit until six months after the last infusion of IMP.

Table 5-1 Highly Effective Contraceptive Methods (from Appendix 1)

Highly Effective Contraceptive Methods Failure rate of $<1\%$ per year when used consistently and correctly.					
Combined (estrogen and progestogen containing) hormonal contraception associated with inhibition of ovulation					
• Oral					
• Intravaginal					
• Transdermal					
Progestogen only hormonal contraception associated with inhibition of ovulation					
• Oral					
• Injectable					
• Implantable					
Intrauterine device (IUD)					
Intrauterine hormone-releasing system (IUS)					
Bilateral tubal occlusion					

Vasectomized partner

A vasectomized partner is a highly effective contraception method provided that the partner is the sole male sexual partner of the female trial participant and the absence of sperm has been confirmed. If not, an additional highly effective method of contraception should be used.

Sexual abstinence

Sexual abstinence is considered a highly effective method only if defined as refraining from heterosexual intercourse during the entire period of risk associated with the study treatment. The reliability of sexual abstinence needs to be evaluated in relation to the duration of the study and the preferred and usual lifestyle of the participant.

- Male trial participants with female partners of childbearing or reproductive potential must agree to use a condom during sexual intercourse from the time of the screening visit until six months after the last infusion of IMP.
- 11. Capable of giving signed informed consent which includes compliance with the requirements and restrictions listed in the informed consent form (ICF) and in this protocol. Patient must have life expectancy of greater than three months.
- 12. A female patient of childbearing potential (see Appendix 1 for definition) must have a negative serum (beta-hCG) pregnancy test at screening.
- 13. A female patient must agree not to donate eggs (ova, oocytes) for the purposes of assisted reproduction while included in the trial and for six months after the last infusion of IMP. Male patients must agree not to donate sperm while included in the trial and for six months after the last infusion of IMP.
- 14. Patient must be willing and able to adhere to the prohibitions and restrictions specified in this protocol.
- 15. Each patient must sign an informed consent form (ICF) indicating that he or she understands the purpose of and procedures required for the trial and are willing to participate in the trial.

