9.2.1 Dose Escalation Part

In the dose escalation part, PET-CT scans must be taken at screening and, if avid at screening, also at Cycle 2 Day 2, and week 12 (\pm 7 days). If a patient, who has been exposed to GEN1029, did not have any PET-CT scans while on treatment and the PET-CT scan at screening displayed avidity, a PET-CT scan should be taken at the end of trial visit (please refer to Section 9.2.3 for additional details on PET-CT scans).

The PET-CT scan at screening is with contrast of thorax, abdomen and pelvis. If there is suspicion of brain metastases or tumors, a scan of the head will be performed before inclusion.

Up to five target lesions (maximum two per organ) will be defined at screening and these must be followed throughout the trial. Non-target lesions will also be assessed throughout the trial.

A CT scan must be performed at Cycle 3, Day 8-14 after first dose. If PET-CT at screening showed no avidity, a CT scan has to be done instead of a PET-CT scan in week 12 (\pm 7 days). From week 18 (\pm 7 days) until week 50 after first dosing, CT scans must be performed every 6 weeks (\pm 7 days), and every 12 weeks (\pm 7 days) thereafter. Imaging assessments should follow calendar days and should not be adjusted for delays in cycle starts.

Additional CT-scans may be performed at the investigators discretion to confirm response or new symptoms. The intervals should not be shorter than four weeks. In this case the investigator must choose the imaging technology based on the clinical indication. Information from additional scans should be added to an unscheduled visit in the eCRF

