11.4.5.1 Secondary Efficacy Endpoints

11.4.5.1.1 Definition of Response

RECIST criteria (v1.1) will be used to define response. Based on the definition of response (Table 11-2) and the combined evaluation (see Table 1 in Eisenhauer et al., 2009), each patient will be assigned 1 of the following categories at each CT scan visit and as Best Overall Response (BOR):

1) CR

2) PR

3) SD

4) PD or

5) Not Evaluable

BOR is the best response recorded from the start of the treatment until disease progression/recurrence (the smallest measurements recorded since the treatment started will be used as the reference for PD).

	Category	Criteria
Based on	Complete	Disappearance of all target lesions. Any pathological lymph nodes must
target lesions	Response (CR)	have reduction in short axis to < 10 mm.
	Partial Response	\geq 30% decrease in the sum of the LD of target lesions, taking as reference
	(PR)	the baseline sum of LDs.
	Stable Disease	Neither sufficient shrinkage to qualify for PR nor sufficient increase to
	(SD)	qualify for PD, taking as reference the smallest sum of LDs while in trial.
	Progressive	\geq 20% (and \geq 5 mm) increase in the sum of the LDs of target lesions, taking
	Disease (PD)	as reference the smallest sum of the target LDs recorded while in trial or the
		appearance of 1 or more new lesions.
	NE	Not evaluable
Based on non-	CR	Disappearance of all non-target lesions and normalization of tumor marker
target lesions		level. All lymph nodes must be non-pathological in size (< 10 mm short
		axis).
	SD	Persistence of 1 or more non-target lesion(s) or/and maintenance of tumor
		marker level above the normal limits.
	PD	Appearance of 1 or more new lesions and/or unequivocal progression of
		existing non-target lesions.
	NE	Not evaluable

 Table 11-2 Definition of Response (RECIST Criteria v1.1)

LD =Longest Diameter; SD for non-target lesions defined as "Non-CR/Non-PD" by Eisenhauer et al., 2009.

Patients with a global deterioration of health status requiring discontinuation of treatment without objective evidence of PD at that time should be classified as having "symptomatic deterioration". Every effort should be made to document the objective progression even after discontinuation of treatment.

Confirmation

SD: follow-up measurements occurring at least 6 weeks (\pm 7 days) after first treatment must have met the SD criteria at least once.

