11.7 Interim Analyses

In the expansion part each cohort will contain of up to 4 stages, targeting a maximum sample size of 60 patients. For each stage, the success of the stage is predicted. If the predictive probability of success is less than 10% the stage is not further explored in order not to expose patients to inefficacious doses based on an interim futility analysis, as detailed in Table 11-3 and Table 11-7. The interim analysis divides each cohort into a maximum of 4 stages in total. The analysis will be based on both the uncomfirmed and confirmed CR or PR observed when the interim-sample size is accomplished.

Stage	Sample size at interim	Sample size at end of stage
	(n)	(N)
1	Not applicable	10
2	10	20
3	20	40
4	40	60

Table 11-3: Cohort stages and Sample Sizes

At the interim, a Bayesian predictive probability approach will be used to evaluate the futility criteria (Lee and Liu, 2008). By using predictive probabilities, it is possible to directly assess the outcome of a trial (in this case stage), if continued to its end (Saville et al., 2014). Given the interim data, the predicted probability is a *weighted average* of posterior probabilities, as if calculated given the outcome at the end of the stage. The weights correspond to how likely each outcome is. The predictive probabilities may in fact be calculated at any time point during Stage 2, 3 and 4.

As originally suggested by Lee and Liu (Lee and Liu, 2008) the predictive probability approach is operated with respect to a historical response rate (p_0) only. However, as applied here, also a target response rate (p_1) that warrants further evaluation of the drug, is being used to evaluate futility. In general, this decreases the Type I error rate and increases the Type II error rate as more studies would be stopped. For more details, please see Section 11.8.2.

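### Inclusion criterion 3, read literally, lowers the 10 mm measurable-lesion minimum on thin-slice CT, where a fall of less than 2 mm can count as a partial response

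*Protocol*

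**What the plan says.** Criterion 3 in Protocol Section 5.1 has two layers. The lead-in cites the standard: "Patients must have measurable disease according to Response Evaluation Criteria In Solid Tumors (RECIST) version 1.1". The bullet beneath it then writes out a size rule for non-nodal lesions: at least one must measure 10 mm or more, "or twice the slice thickness if slices are not 5 mm thick". Lymph nodes have their own rule of 15 mm in the shortest diameter.

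Sections 9.2.1 and 9.2.2 govern target-lesion selection and add no minimum size: "Up to five target lesions (maximum two per organ) will be defined at screening". The documents prescribe no slice thickness. Scans are read by a local radiologist (Section 9.2.4).

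In Table 11-2 (Section 11.4.5.1.1) partial response needs a "30% decrease in the sum of the LD of target lesions" relative to baseline, with no minimum in millimetres. Progression in target lesions needs a relative increase of at least 20% and also an absolute increase of at least 5 mm.

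On confirmation, the expansion part's primary ORR uses confirmed responses (Section 11.5.1.1). The interim futility look does not: "The analysis will be based on both the uncomfirmed and confirmed CR or PR observed when the interim-sample size is accomplished" (Section 11.7). The SAP (Sections 15.3 and 15.4) makes confirmed response the main analysis and adds a supportive analysis of confirmed and unconfirmed responses together. SAP Section 3 states that the expansion part was not initiated, and Section 3.3 gives 48 subjects in all.

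**The concern.** The alternative to 10 mm applies whenever slices differ from 5 mm, in either direction. For thicker slices it raises the minimum, which is sensible. For thinner slices it lowers it, which undoes the 10 mm minimum in the same sentence. A site that follows the text with thin-slice CT could enrol a patient whose only target lesion is a few millimetres across.

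The response rules then treat small lesions unevenly. A sole 5 mm lesion reaches partial response on a 1.5 mm fall, but reaches target-lesion progression only by growing 5 mm, that is, by doubling. Progression through new or non-target lesions is unaffected. Measurement error in such a lesion can therefore register as a response far more easily than as progression. The outputs exposed are ORR, best overall response, the supportive analysis of all responses and the waterfall plots. In at most 48 subjects, one spurious response is visible.

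**Working it through.** **Inputs from the documents.** Size rule: 10 mm, or 2 × slice thickness when slices are not 5 mm (Section 5.1). Partial response: 30% fall from the baseline sum (Table 11-2). One lesion is enough to qualify.

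**Step 1: the plan's own figure.** At 5 mm slices, 2 × 5 = 10 mm, so the two halves of the rule agree there and only there.

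**Step 2: the literal rule at other thicknesses.** Minimum = 2 × slice thickness. The fall needed for partial response in a sole lesion at that minimum = 0.30 × minimum.

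| Slice (mm) | Minimum lesion (mm) | Fall giving PR (mm) |
|---|---|---|
| 1 | 2 | 0.6 |
| 2 | 4 | 1.2 |
| 2.5 | 5 | 1.5 |
| 3 | 6 | 1.8 |
| 5 | 10 | 3.0 |
| 7 | 14 | 4.2 |

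This step needs no assumption.

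**Step 3: how often error alone gives a partial response.** The documents give no measurement error, so the following are assumptions: one target lesion of true size L, no true change, and independent normal error of standard deviation SD at every scan, baseline included. A response is read when follow-up ≤ 0.7 × baseline. The quantity (follow-up − 0.7 × baseline) has mean 0.3L and variance SD² × (1 + 0.7²) = 1.49 SD². Hence

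P(false PR at one scan) = Φ(−0.3L / (SD × √1.49)).

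Example: L = 5, SD = 1.0 gives Φ(−1.5 / 1.2207) = Φ(−1.229) = 0.110. For L = 10 and the same SD, Φ(−3.0 / 1.2207) = Φ(−2.458) = 0.007.

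For a response read on both of two follow-up scans, the shared baseline error makes the two readings correlated. Those figures come from simulation (400,000 draws).

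| L (mm) | One scan, SD 0.5 / 1.0 / 1.5 mm | Both of two scans, SD 0.5 / 1.0 / 1.5 mm |
|---|---|---|
| 2 | 16% / 31% / 37% | 4.9% / 14% / 19% |
| 5 | 0.7% / 11% / 21% | <0.1% / 2.7% / 7.3% |
| 10 | <0.1% / 0.7% / 5.1% | <0.1% / <0.1% / 0.8% |

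**Step 4: ratio of 5 mm to 10 mm at one scan.** At SD 1.0 mm, 0.1096 / 0.0070 ≈ 16. At SD 1.5 mm, 0.2063 / 0.0507 ≈ 4. At SD 0.5 mm the 5 mm risk is itself only 0.7%.

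Confirmation lowers the risk but does not remove it, because a baseline that was read too large counts toward response at every later scan.

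**The case against.** Four points weigh on the other side.

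- **The lead-in governs.** The criterion opens by requiring measurable disease under RECIST 1.1, and the bullet does not say that it replaces that standard. Sites may simply apply RECIST. This stands in part: the documents do not reproduce the RECIST definition of measurability, so they cannot show whether the lead-in restores 10 mm. What they do show is a written size rule that some sites could follow and others could override, which is reason enough to reconcile the two.
- **Confirmation protects the reported endpoint.** This largely stands. The SAP's main response analysis is confirmed, so the two-scan column is the relevant one, and single-scan risks apply only to the supportive analysis and the waterfall plots.
- **Error may shrink with slice thickness.** The risk depends only on L/SD. A 5 mm lesion with SD 0.5 mm has the same 0.7% as a 10 mm lesion with SD 1.0 mm. If error fell in proportion to thickness, the literal rule would cost nothing. This cannot be excluded from the documents. It is the reason for showing a range.
- **Most patients will have larger lesions.** With up to five targets in advanced disease, a small lesion matters only when it is alone or dominates the sum. This stands, and the share of subjects concerned is unknown.

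It is also fair that rewording eligibility changes little for a trial reported at 48 subjects, and that an existing listing already holds the lesion data.

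**Conclusion.** The wording defect is real and rests on arithmetic alone: for slices under 5 mm the literal rule drops below the 10 mm minimum beside it, and no other written passage restores that minimum. The size of the consequence is conditional. For a sole 5 mm lesion with no true change, the false-response risk on two scans is <0.1% to 7.3% over the assumed SD range, against <0.1% to 0.8% at 10 mm.

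A reader might infer three stronger things that the documents do not support:

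- **That the trial's primary ORR and futility decisions were inflated.** Those belong to the expansion part, which was not initiated. Its primary ORR was to use confirmed responses, and Section 11.8.2 treats the interim response counts as a guideline. As designed, unconfirmed responses could have entered those counts. In practice only the escalation part's secondary efficacy outputs are exposed, and its DLT endpoint is untouched.
- **That the false-response risk rises 7- to 50-fold.** That range follows from placing an error SD of 1.0–1.5 mm on the change itself, at a single scan (6.7%–15.9% at 5 mm against 0.1%–2.3% at 10 mm). With error at each scan and the same SD range the ratio is about 4 to 16, and at SD 0.5 mm the absolute risk is negligible.
- **That patients with such lesions were enrolled.** Nothing in the documents shows this either way.

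This should be corrected, but it does not threaten the trial's main conclusion.

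**What to change.** **Protocol, Section 5.1, criterion 3.** Limit the alternative in the parenthesis to slices more than 5 mm thick. It then agrees with the 10 mm minimum in the same sentence and can only raise it. Check the resulting text against the cited RECIST 1.1 definition so that the lead-in and the bullet give one rule.

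**SAP.** In the existing RECIST lesion listing (16.02.02.02.a), add a flag for any subject whose baseline target lesions were all below the minimum: 10 mm longest diameter, or 15 mm short axis for nodes. If any subject is flagged, report confirmed ORR with and without the flagged subjects. If none is, one sentence in the report closes the matter.

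**Cost.** A few words in the protocol and one derived variable. A few patients whose only lesions are below 10 mm would become ineligible under any further use of the criterion. No extra scans are needed.
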